8.3 Prohibited Therapy During Trial Period

The following medications are prohibited both prior to and during the trial, as stated below. However, any patients taking these medications after starting treatment on the trial should not be withdrawn from the trial unless there are safety concerns. If applicable, the possible effects of these medications on the trial endpoints will be considered during the assessment of the evaluable period (see Section 13.6.1).

- Any new non-pharmacological interventions for epilepsy (including ketogenic diet and any neurostimulation devices for epilepsy) or changes in regimen during the pilot and pivotal phases of the trial (and within the 2 weeks prior to the screening visit).
- Clobazam and oral mTOR inhibitors during the pilot and pivotal phase of the trial (and within the 2 weeks prior to the screening visit).
- Recreational or medicinal cannabis, or synthetic cannabinoid-based medications (and within the 1 month prior to the screening visit).
- Any other IMP taken as part of a clinical trial (and within a minimum of 5 half-lives prior to the screening visit).

Furthermore, any increases to existing AEDs or commencement of new AEDs during the pilot or pivotal phase may result in the patient being withdrawn from the trial.

8.4 Compliance in Investigational Medicinal Product Administration

The patient's caregiver will record IMP intake on each treatment day in the paper diary. Caregivers should return all IMP (used and unused) at each of Visits 4, 6–12, and the end of taper period visit, if applicable. The diary-reported dosing information will be checked and any discrepancies discussed with the patient's caregiver at the time of the visit and documented accordingly within the patient's source documents. Records of IMP accountability will be maintained according to Section 5.3.4.

8.5 Access to Blinded Treatment Assignment (Pivotal Phase Only)

The identity of IMP assigned to patients in the pivotal phase will be held by the IVRS/IWRS. The principal investigator (PI) at each site, or his/her designee, is responsible for ensuring that information on how to access the IVRS/IWRS for an individual patient is available to the relevant staff in case of an emergency and unblinding is required. A patient's treatment assignment should only be unblinded when knowledge of the treatment is essential to make a decision on the medical management of the patient. Unblinding for any other reason will be considered a protocol deviation.

EudraCT Number: 2015-004904-50

Protocol V3 20Sep16

The investigator is encouraged to contact GW to discuss the rationale for unblinding prior to doing so. However, to prevent delays to the investigator or medical personnel responding to a potentially emergent situation, unblinding of trial medication will not be dependent upon the investigator receiving approval from GW (i.e., the investigator will be able to obtain the code break information independent of contacting GW).

If the investigator does unblind, they must contact GW within 1 working day of the event and must document the time, date and reason(s) for unblinding in the patient's medical notes and on the CRF.

9 TRIAL PROCEDURES

A list of the required trial procedures is provided in the subsections that follow; refer also to the schedule of assessments (APPENDIX 1). Assessments or tests that are not done and examinations that are not conducted must be reported as such on the CRF.

The location of the source data for the following procedures will be documented, per site, in a signed source data verification plan; for further details see Section 16.2.

9.1 Trial Procedures by Visit

Patients and their parent(s)/legal representative will be invited to take part in the trial and will be issued with the parent(s)/legal representative information and ICF. Following adequate time to discuss the trial with the investigator, nurse, relatives, or caregiver, as wished, patients of those parent(s)/legal representatives who provide written informed consent will be screened for entry into the trial.

9.1.1 Pilot and Pivotal Phase

9.1.1.1 Visit 1 (Day −7 to −1): Screening

Following collection of parent(s)/legal representative informed consent (Section 9.2.1), patients will be assigned a unique patient number using an IVRS/IWRS (Section 9.2.2). The following will then be collected/assessed within a screening period which must be no more than 7 days in duration, during which time patients must continue to take their current IS therapy at a stable dose:

- Eligibility criteria (Section 6).
- Patient demographics (Section 9.2.3).
- Full medical history (Section 9.2.4).
- Concomitant medication review (Section 9.2.5).
- Physical examination (Section 9.2.6).
- Vital signs (Section 9.2.7).
- ECG (Section 9.2.8).
- Video-EEG (Section 9.2.9).
- Clinical laboratory samples (blood and urine [if possible]; Section 9.2.10) for:
 - Serum biochemistry.
 - Hematology.

- Urinalysis.

To minimize the volume of blood required, serum biochemistry and hematology results from samples analyzed up to 3 days prior to Visit 1 may be used.

- AEs (Section 12).
- Caregiver paper diary issue and training (Section 9.2.13). The caregiver will be required to record all AEs, concomitant AEDs and rescue medications, seizures, and spasms from the time of consent.

Patients can be re-screened only once, in exceptional cases, at the discretion of the investigator and GW medical monitor.

9.1.1.2 Visit 2 (Day 1 [+3 Days])

This visit will occur up to 7 (+3) days after Visit 1 (screening). Patients who satisfy all eligibility criteria (Section 6) during the screening period will be assigned GWP42003-P (pilot phase) or randomly allocated to GWP42003-P or matching placebo (pivotal phase) using the IVRS/IWRS (Section 9.2.2). Eligible patients must begin treatment within 7 days of their video-EEG screening assessment. The following will be collected/assessed prior to the patient receiving IMP:

- Concomitant medication review (Section 9.2.5).
- Physical examination (Section 9.2.6).
- Vital signs (Section 9.2.7).
- CGIC memory aid (Section 9.2.12.1).
- PGIC memory aid (Section 9.2.12.2).
- Vineland-II (Section 9.2.12.3).
- Caregiver diary review (Section 9.2.13) for:
 - Spasm/seizure information.
 - Changes in concomitant AEDs.
 - Usage of rescue medication.
 - AEs.
- AEs (Section 12).

Patients will receive sufficient IMP for 2 weeks of dosing. Patients in the pilot phase will remain in the clinic as inpatients during the 4-day titration period. For all patients, the first dose of IMP will be taken in the clinic on the morning of Day 1 with

EudraCT Number: 2015-004904-50

Protocol V3 20Sep16

an ECG assessment between 3 and 5 hours postdose (Section 9.2.8). For patients involved in the pivotal phase of the trial, a PK blood sample will be taken, provided the risk/benefit outcome is favorable in the investigator's opinion (Section 9.2.11). If a PK blood sample is collected, the investigator must note the sampling time and the dosing times of IMP and of any concomitant AEDs taken that day and the previous day. Patients will titrate to their target dose of GWP42003-P (or equivalent volume of placebo in the pivotal phase; Section 8.1.2) and will continue at this dose, or the highest tolerated dose up to 40 mg/kg/day, for the remainder of the 2-week treatment phase. During this time, the patient's current IS therapy may be continued or tapered, at the discretion of the investigator. All non-pharmacological interventions for epilepsy (including ketogenic diet and any neurostimulation devices for epilepsy) must remain stable during the pilot and pivotal phases of the trial. Following Visit 2, daily safety checks will be made during the first week of IMP dosing.

9.1.1.3 Daily Safety Checks (Day 2 to Day 7 [Inclusive])

Safety checks will be made daily (including weekends, where possible) from Day 2 to Day 7 (inclusive). Safety checks can be conducted by telephone (where applicable they will be incorporated into scheduled visits, e.g., Visit 3 [Day 4]). During each safety check, caregivers will be asked about the following, along with confirmation that the relevant details have been recorded in the caregiver diary:

- Spasm/seizure information.
- Changes in concomitant AEDs.
- Usage of rescue medication.
- AEs.

Confirmation that the safety check has taken place will be recorded in the CRF.

9.1.1.4 Visit 3 (Day 4 [+1 Day])

This visit will occur 3 (+1) days after Visit 2. The following will be collected/assessed:

- Concomitant medication review (Section 9.2.5).
- Vital signs (Section 9.2.7).
- ECG (prior to the day's first dose of IMP; Section 9.2.8).
- Clinical laboratory samples (blood and urine [if possible]; Section 9.2.10) for:
 - Serum biochemistry.

- Hematology.
- Urinalysis.
- Caregiver diary review (Section 9.2.13) for:
 - Spasm/seizure information.
 - IMP usage.
 - Changes in concomitant AEDs.
 - Usage of rescue medication.
 - AEs.
- AEs (Section 12).

All patients will take their IMP in the clinic with an additional ECG assessment between 3 and 5 hours postdose (Section 9.2.8). Patients in the pilot phase will then be discharged from the clinic.

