3.3.1 Selection of Study Dose

Standard treatment regimens with currently approved IS therapies involve achieving high maintenance dose levels rapidly⁴⁹. For example, VGB is initially given at a dose of 50 mg/kg/day and can be titrated by 25–50 mg/kg/day increments every 3 days to a maximum dose of 150 mg/kg/day⁵⁰; both of these doses are approximately 3 times the recommended initial and maximal dose of VGB in adults. Moreover, treatment with ACTH, which is injected intramuscularly, begins at the maintenance dose immediately (150 IU/m²/day recommended)⁵¹. Consequently, due to the urgency required in achieving efficacious doses to treat this population, rapid titration to a maximal safe and tolerable maintenance dose is proposed in this trial in infants with IS. The titration regimen proposed for use on this trial was discussed, and agreed, with consultants. Due to the rapid titration of the IMP, all patients in the pilot phase will be inpatient during the 4-day titration period. Following independent data safety monitoring committee (DSMC) review, adjustment of doses and dose regimens may occur during the trial, as well as plans for the dose titration during the pivotal phase.

The DSMCs of the GW studies in Dravet syndrome patients (GWEP1332, GWEP1424) and LGS patients (GWEP1414, GWEP1423) recommended a target of 20 mg/kg/day as a safe and tolerable dose during a 14-week treatment period. The lower age limit in these studies is 2 years of age. Three of the 4 studies are now complete; preliminary data from the GWEP1332 trial show GWP42003-P was generally well tolerated. The most common AEs (occurring in greater than 10% of GWP42003-P-treated patients [n=61]) were: somnolence, diarrhea, decreased appetite, fatigue, pyrexia, vomiting, lethargy, upper respiratory tract infection and convulsion. Of those patients on GWP42003-P for whom an AE was reported, 84% of these AEs were mild or moderate.

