Patients will enter the pilot and pivotal phases at the respective screening visits (Visit 1, Day -7 to -1) for assessment of eligibility, which includes a prolonged video-EEG. Patients who satisfy all eligibility criteria will then be administered GWP42003-P (pilot phase) or randomized to GWP42003-P (1 of 2 dose levels) or placebo at a 1:1:1 ratio (pivotal phase) (Visit 2, Day 1 [+3 days]). The High Dose Level will be as recommended by the DSMC; the Low Dose Level will be defined as 50% of the High Dose Level. Patients in the placebo group will be split into 2 equivalent cohorts: half receiving Low Dose Level dosing volumes and half receiving High Dose Level dosing volumes. Following baseline assessments, patients will titrate the IMP in 10 mg/kg/day increments to the target dose level (or equivalent volume of placebo in the pivotal phase) and will continue at this dose, or the highest tolerated dose up to 40 mg/kg/day, for the remainder of the 2-week treatment phase. Patients in the pilot phase will remain in the clinic as inpatients during the 4-day dose titration period. If deemed safe by the DSMC then it is planned for those in the pivotal phase to titrate in an outpatient setting. Further clinic-based assessments will take place after 3 days' dosing (Visit 3, Day 4 [+1 day]). All patients in the pilot and pivotal phases will return to the clinic after 2 weeks' dosing (Visit 4, Day 15 [+3 days]) or earlier if they withdraw prematurely. All patients who complete

EudraCT Number: 2015-004904-50

Protocol V3 20Sep16

treatment will then have the opportunity to receive GWP42003-P during the subsequent OLE phase. The OLE phase will last for a maximum of 1 year.

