8.1.2 Dose Escalation and Dose Adjustments

All patients will be weighed during each clinic visit where IMP is dispensed (i.e., no physical exam performed at Visit 3 [Day 4] or Visit 5 [Day 19]). The volumes of IMP solution to be taken each day during the titration periods, and for the remainder of each phase of the trial, will be calculated and provided to the patient's caregiver. If an unacceptable AE develops at any time during the titration periods, dosing should initially be amended or suspended, at the investigator's discretion, until the event has resolved or is well tolerated. During the maintenance periods, patients should continue on a stable dosing regimen at the target dose. However, if the patient is not able to tolerate the target dose, the investigator may consider temporarily or permanently reducing the dose or dosage for the remainder of the maintenance period.

Eligible patients will be assigned GWP42003-P (pilot phase) or randomly allocated to GWP42003-P or matching placebo (pivotal phase) and will titrate the IMP over 4 days according to the titration regimen, an example titration regimen up to

EudraCT Number: 2015-004904-50

Protocol V3 20Sep16

40 mg/kg/day over 4 days is shown in Table 8.1.2-1. Patients in the pilot phase will remain in the clinic as inpatients during the 4-day titration period. If the DSMC confirms it is safe then patients in the pivotal phase will titrate the IMP as outpatients. For the pivotal phase there will be 2 dose levels; the High Dose Level will be as recommended by the DSMC, the Low Dose Level will be defined as 50% of the High Dose Level. Patients in the placebo group will be split into 2 equivalent cohorts: half receiving Low Dose Level dosing volumes and half receiving High Dose Level dosing volumes. In both phases, daily safety checks will be made during the first week of IMP dosing.

Table 8.1.2-1 Exam	ble 8.1.2-1 Example Titration Regimen: Pilot and Pivotal Phase					
Day	IMP Dosage	Total Daily IMP Dose ²				
1	5 mg/kg (am/pm)	10 mg/kg				
2	10 mg/kg (am/pm)	20 mg/kg				
3	15 mg/kg (am/pm)	30 mg/kg				
4 onwards	20 mg/kg (am/pm)	40 mg/kg				

¹Volumes of IMP to be taken each day will be calculated using the patient's weight and the required dose.

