9.2.7 Vital Signs

Vital signs measurements (systolic and diastolic blood pressure, pulse rate, body temperature and respiratory rate), taken in a supine position at rest for 5 minutes, will be completed alongside the physical examination. The methods/procedures employed for vital signs measurements must be consistent throughout the trial, where possible. Any deviation in methods used must be reported to the study monitor.

9.2.8 12-lead Electrocardiogram

ECG recordings will be performed after 5 minutes in a supine position. A physician must review the ECG immediately (annotated, signed and dated) and any abnormal findings considered to indicate significant medical history or AEs must be recorded appropriately on the CRF. Additional ECG measurements can be taken at any time during the trial, if clinically indicated.

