													(+3 days)	(+3 days)
Changes in concomitant AEDs		X	X	X	X	X	X	X	X	X	X	X	X	X
Usage of rescue medication		X	X	X	X	X	X	X	X	X	X	X	X	X
AEs		X	X	X	X	X	X	X	X	X	X	X	X	X

All patients in the pilot phase will titrate GWP42003-P in an inpatient setting. In both phases (pilot and pivotal), daily safety checks will be made during the first week of IMP dosing (can be conducted by telephone). Each safety check will conduct the same assessments as listed for safety follow-up visit.

²Daily safety checks will be made during the first week of OLE IMP dosing (can be conducted by telephone). Each safety check will conduct the same assessments as listed for safety follow-up visit.

³IMP is to be tapered over 10 days following discontinuation of IMP, end of treatment, or withdrawal (unless continued dosing is not possible due to an AE).

⁴Safety follow-up visit is to occur 28 (+3) days after date of final dose (including tapered dose); weekly (±3 days) telephone calls must be made during the follow-up period. Each safety telephone call will conduct the same assessments as listed for safety follow-up visit.

⁵Based on assessment of clinical laboratory and video-EEG results.

⁶ECG to be performed between 3 and 5 hours after the day's first dose of IMP only.

⁷ECG to be performed both prior to the day's first dose of IMP and between 3 and 5 hours after this dose.

⁸Only for patients involved in the pivotal phase, and progressing to the OLE from the pivotal phase. To be conducted only if the risk/benefit outcome is favorable, in the investigator's opinion.

Memory aid only (worksheet completed).

¹⁰If necessary, IMP will also be dispensed for taper period.

¹¹IMP usage to be recorded on a dosing schedule which will form part of the paper diary

EudraCT Number: 2015-004904-50

Protocol V3 20Sep16

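### Pilot discharge at Visit 3 carries no dose condition, so an infant whose titration was held can take the first target-level dose at home; make discharge depend on completed titration

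*Protocol*

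**What the plan says.** **Discharge.** Section 9.1.1.4 places Visit 3 at 3 (+1) days after Visit 2, so on Day 4 or Day 5. The infant has a predose ECG, takes a dose in clinic and has a second ECG 3 to 5 hours later. Then: "Patients in the pilot phase will then be discharged from the clinic". The synopsis text for Visit 3 says the same. Neither place mentions the dose reached.

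**Inpatient titration.** Appendix 1, footnote 1, is unconditional: "All patients in the pilot phase will titrate GWP42003-P in an inpatient setting". The note to Figure 1-1 and SAP Table 1 repeat the rule. Section 3.3.1 gives the reason: "Due to the rapid titration of the IMP, all patients in the pilot phase will be inpatient during the 4-day titration period". Sections 4.1, 8.1.2 and 9.1.1.2 likewise describe a 4-day inpatient period.

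**Holds.** If an unacceptable adverse event occurs during titration, Section 8.1.2 says "dosing should initially be amended or suspended", at the investigator's discretion, until the event resolves or is well tolerated. It sets no time limit and does not say what happens to the inpatient stay.

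**After discharge.** Daily safety checks run to Day 7 and may be by telephone (Section 9.1.1.3). The next scheduled ECG is at Visit 4, Day 15 (+3) (Section 9.1.1.5).

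**The concern.** The discharge sentence follows the calendar, while the inpatient rule follows titration. They agree when titration runs to plan and part company when it is held. The infant affected has just had an adverse event serious enough to interrupt dosing. If site staff follow Section 9.1.1.4 literally, that infant can take the final step, from 30 to 40 mg/kg/day, at home.

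What is lost is a target-level dose observed in clinic and an ECG 3 to 5 hours after it. The withdrawal rule in Section 10 (QTcB of 500 msec or more, or a shift of 60 msec or more from baseline) would then have no scheduled target-level reading to act on until Visit 4.

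**Working it through.** **Inputs**
- Pilot titration: 10, 20, 30 and 40 mg/kg/day on Days 1 to 4, given twice daily (synopsis dose text; Table 8.1.2-1).
- Visit 3: Day 4 or 5. Discharge can follow the morning dose and the 3 to 5 hour ECG (Section 9.1.1.4). The evening dose comes at least 8 hours after the morning one (Section 8.1.1).
- Visit 4: 14 (+3) days after Visit 2, so Day 15 to 18.

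**The plan's own figure.** 10 + 3 × 10 = 40 mg/kg/day on Day 4, and 2 × 20 = 40. Table 8.1.2-1 is reproduced.

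**Assumption.** A hold of h days comes before the last step, and titration then resumes stepwise. The first target-level day is Day 4 + h.

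**Target-level doses on that first day that are sure to be in clinic**

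| Hold (days) | First target day | Visit 3 on Day 4 | Visit 3 on Day 5 |
|---|---|---|---|
| 0 | Day 4 | 1 of 2 | 2 of 2 |
| 1 | Day 5 | 0 of 2 | 1 of 2 |
| 2 | Day 6 | 0 of 2 | 0 of 2 |
| 3 | Day 7 | 0 of 2 | 0 of 2 |

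In the 0-of-2 cells the Visit 3 ECG is taken below the target dose.

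**Time from the first target-level dose to the first scheduled ECG at that dose, in the 0-of-2 cells**
- 1-day hold, Visit 3 on Day 4: 15 − 5 = 10 to 18 − 5 = 13 days.
- 2-day hold: 15 − 6 = 9 to 18 − 6 = 12 days.
- 3-day hold: 15 − 7 = 8 to 18 − 7 = 11 days.

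**Comparison.** An infant with no hold and Visit 3 on Day 4 also goes 15 − 4 = 11 to 18 − 4 = 14 days without a scheduled ECG. The length of the gap is therefore not what sets the held infant apart. The difference is that the infant without a hold enters the gap with a target-level ECG already read.

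**No hold.** With a Day 4 visit, only the evening 20 mg/kg dose may fall at home. It equals the morning dose just observed in clinic with an ECG.

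**The case against.** The strongest reply is that the protocol already answers the question. Appendix 1 is categorical about inpatient titration, so sending an infant home with a step outstanding would breach it. Read together, Visit 3 is simply the nominal end of titration. An investigator may keep the infant in, and Section 9.2.8 allows extra ECGs at any time. A held infant may also settle at a lower dose and never take the last step.

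Much of this stands. The gap needs a hold, a return to upward titration, and discharge before the final step. What does not stand is the claim that the text settles the matter. The discharge sentence is just as unconditional, and it sits in the visit instructions that sites follow. The phrase about a 4-day period does not stretch, and an extra ECG or a longer stay is permitted but not required.

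Three stronger readings are tempting, and the documents do not support them:
- *Every pilot infant goes home without the target dose being observed.* With no hold, the first target dose is in clinic with an ECG, and a 1-day hold with a Day 5 visit gives the same protection.
- *The DSMC would judge outpatient titration without target-dose data.* Section 8.1.2 says "If the DSMC confirms it is safe then patients in the pivotal phase will titrate the IMP as outpatients", but under Section 14 the committee reviews pilot safety data from the whole 2-week treatment phase, once each cohort has completed Day 15.
- *Infants were probably affected.* The documents give no rate of titration holds, so no frequency can be stated.

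**Conclusion.** The concern holds in a narrow form. Section 9.1.1.4 and Appendix 1 give conflicting instructions for pilot infants with a 1-day hold and Visit 3 on Day 4, or a hold of 2 days or more on either visit day. Following the discharge sentence puts the first target-level dose at home, with 10 to 13 days (1-day hold) or 9 to 12 days (2-day hold) before a scheduled ECG at that dose. The other branches raise no material concern.

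This rests on stepwise resumption after a hold and on the infant going on to the target dose. Severity is low. SAP Section 5 states that only the open-label pilot was included, and SAP Section 4.1 gives 9 patients. The point concerns the protocol text and any reuse of it, not the analysis or the conclusions drawn from it.

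**What to change.** Pilot phase only. Leave the timing and assessments of Visit 3 unchanged.

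1. In Section 9.1.1.4 and the synopsis text for Visit 3, keep "Patients in the pilot phase will then be discharged from the clinic" and extend it with: *once titration is complete, i.e., once the first dose at the target dose, or at the highest tolerated dose chosen by the investigator, has been given in the clinic with an ECG 3-5 hours postdose.*
2. In Section 8.1.2 add: *If titration is delayed or amended in the pilot phase, any remaining upward dose step is given as an inpatient.*

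Because the condition refers to the first dose at the final level, it also works if dosing is changed to three times daily.

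**Cost.** Nothing changes for infants without a hold, or with a 1-day hold and Visit 3 on Day 5. Otherwise the added stay is (4 + h) minus the Visit 3 day: one night for a 1-day hold with a Day 4 visit, and two nights or one for a 2-day hold with a Day 4 or Day 5 visit. At most one routine ECG is added. Section 8.1.2 does not limit the length of a hold, so the added stay has no fixed limit either, but the investigator can end it by settling on the highest tolerated dose. The planned interval to Visit 4 without a scheduled ECG remains. No SAP change is needed.
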